Specific Aim 1: To investigate that increased DA transmission normalizes reward responsiveness and optimism in females with histories of CSA. We will use reward paradigms from our pilot work in conjunction with a pharmacological challenge to test that decreased phasic DA transmission within mesolimbic regions plays a key role in CSA sequelae. We hypothesize that increased phasic DA release – achieved through presynaptic DA autoreceptor blocking by means of single low dose of the D₂/D₃ antagonist amisulpride – will improve positive reinforcement learning and boost activation in reward-related brain regions, particularly the ventral and dorsal striatum (**Hypothesis 1a**). Due to hypothesized downregulation of mesolimbic DA pathways, we expect that individuals with CSA and current MDD (“CSA/MDD”) will show the largest improvements. Confirming that a well-functioning reward system is a marker of resilience, adults with CSA without lifetime psychopathology (“CSA/RES”) will show normative activation and performance under placebo (**Hypothesis 1b**). We also hypothesize that increased phasic DA release – achieved through amisulpride – will re-orient MDD individuals from a pessimistic outlook to an optimistic outlook as measured by the Optimism Bias Task (**Hypothesis 1c**). In addition, under placebo, MDD participants will show a pessimistic outlook as compared with healthy controls (**Hypothesis 1d**).

Specific Aim 2: To investigate dopamine transporter and its relation to reward processing in females with CSA history. We will utilize positron emission tomography (PET) and a highly selective radioactive ligand (¹¹C-altropane) to assess DAT binding in CSA adults. Animal studies have shown that early adversity leads to DAT downregulation within mesolimbic regions. In humans, we have observed links between altropane binding and depressive symptoms, the most common CSA sequelae). Based on our data, we expect that, relative to control and CSA/RES subjects, CSA/MDD adults will show reduced altropane binding (**Hypothesis 2a**). We further hypothesize that, among the CSA/MDD group, reduced DAT will correlate with blunted reinforcement learning and striatal activation (**Hypothesis 2b**).

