Saliva samples will be acquired for cortisol assessment 20 min after arrival (baseline saliva sample), immediately following the stress manipulation (acute saliva sample), following block 1 of the second PRT (post-stressor saliva sample #1), following block 2 of the second PRT (post-stressor saliva sample #2), and 68 minutes following the stress manipulation (recovery saliva sample). Saliva samples will be collected using passive-drooling cryovials (Salimetrics, State College, PA, USA). Subjects will be instructed to not eat, drink, smoke, brush their teeth or engage in physical activity for at least 30 min before the session. To avoid contamination from food particles, water will be handed to rinse oral cavities prior to data collection. In our prior work, intra- and inter-assay coefficients of variance were <10% (Koslov et al 2011). The protocol is in line with large cortisol studies (e.g., Lederbogen et al 2010) and adheres to the policies on tissue storage and transfer of McLean Hospital.

fMRI Session

This session will take place at the McLean Hospital Imaging Center. Participants will complete the Monetary Incentive Delay (MID) task during fMRI (collected using the 3T MR scanner). Because the pharmacokinetics of amisulpride are linear and a first peak plasma concentration is seen 1-1.5 hr after oral administration (Curran & Perry 2001), fMRI scanning will start 1 hr after administration of amisulpride (or placebo). The dose (50 mg) was selected based on prior studies (e.g., Hamon-Vilcot et al 1998; Samuels et al 2006), and the observation that all prior studies in depressive disorders have used 50 mg/day doses. Using a double-blind design, half of the participants in each group will be administered amisulpride (or placebo).

Amisulpride is a substituted benzamide neuroleptic with high affinity for D₂/D₃ DA receptors and low affinity for other receptors, and higher binding to DA receptors in limbic (e.g., NAc) than nigrostriatal regions. Animal studies have shown that at low doses, amisulpride preferentially blocks presynaptic DA autoreceptors, leading to increased DA synthesis and release and prohedonic effects (Coukell et al 1996; Schoemaker et al 1997).

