This session will take place at the Massachusetts General Hospital PET facility. After re-screening for compatibility with the PET environment, any remaining questions will be answered. Subjects will then be positioned in the gantry of a PET camera. Head alignment will be made, relative to the canthomeatal line, using projected laser lines. A Civco vac-lok cushion with velcro head strap will be used to prevent movement. A peripheral venous catheter will be inserted for radiopharmaceutical injection. 9 mCi of [¹¹C] altropane will be injected either by a physician or a trained nuclear medicine technicians and PET scanning will begin. The minimum specific activity that we use for C-11 altropane is 300 mCi / micromole at time of administration. PET data will be acquired using an ECAT EXACT HR + PET camera.

Subjects will be instructed that they are being continuously monitored and can be heard by the investigators if there is a problem. They will also be reminded that it is best for them to remain still

and refrain from any head, face or jaw movements. After conclusion of the PET scan, participants will be removed from the scanner.

Compared to other DAT tracers, altropane offers the following advantages (Fischman et al 2001; Madras et al 1998a,b,c): (1) rapid (max. accumulation 15-30 min post-injection) and specific striatal binding; (2) high selectivity for DA sites; (3) reversible binding kinetics; and (4) a relatively low level of nonspecific binding.

Prior to the PET scan, a blood serum pregnancy test and a urine drug will be administered, and participants will complete two tasks on cognitive functioning: the Optimism Bias Task, and the Self-Concept Attention Task.

Optimism Bias Task

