Subjects will be paid \$15/hour for the SCID session (session 1), up to \$70 for the ERP session including \$38 for completing the EEG and up to \$32 on the probabilistic reward task, up to \$150 for the fMRI session including \$100 for completing the session and up to \$50 on the MID task, and \$200 for the PET session. In addition, participants who complete all four sessions of the study will earn an additional \$75. Lastly, if participants complete only part of a study session, they will be compensated in a prorated manner, such that if they complete half of a study session, they will be compensated half of the total amount (e.g., participant completes half of the PET scan session, he/she will be compensated \$100). If the participant completes all of the sessions, they can earn up to \$555. The subset of subjects who participate in the additional skin fibroblast study (n=20) will be compensated \$100.

Randomization

For protocol 2010-P-002593, all subjects in study are administered a single low dose of amisulpride (50 mg) in order to test the role of dopaminergic mechanisms in the pathophysiology of MDD. This proof-of-mechanism study uses a double-blind, placebo-controlled between-subject design (for each group in study, 50% of the subjects in each group will receive placebo, with the remaining 50% receiving a single dose of amisulpride), involves a single MRI session, and does not include a treatment component. Though data collection has not yet been completed, the blind was broken as of May 2016 to conduct preliminary analyses. Accordingly, the medication blind will be broken as of November, 2016 in order to allow further analyses. In order to preserve the scientific integrity of the study, we propose the following precaution:

The Research Assistant responsible for running participants ([name]), the study doctors ([name], [name]), and any other member of the [name] Lab who directly interacts with participants will remain blind to drug group assignment. Accordingly, if we discover during statistical analyses that a few participants yielded unusable data (e.g., due to excessive motion artifacts), we will be able to enroll and test a few final participants in a fully unbiased way.

b. Drugs to be used

Amisulpride

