Procedure: Because the pharmacokinetics of amisulpride are linear and similar across gender, and a first peak plasma concentration is seen 1-1.5 hr after oral administration (Ascalone et al, 1996), fMRI scanning will start 1 hr after administration of amisulpride (or placebo). During the one-hour wait between the administration of amisulpride (or placebo), participants may read or view a neutral film. During this time, experimenters will carefully monitor participants to assess the presence/absence of side effects. A designated study physician will be present at the neuroimaging facility throughout the session with a response time of 2-3 minutes in case study participants experience adverse side effects during the fMRI scanning. After one hour, participants will be asked to enter the scanner, and data collection will begin. The dose (50 mg) was selected based on prior studies (Hamon-Vilcot et al., 1998; Samuels et al, 2006), and the observation that all prior studies using amisulpride in depressive disorders have used 50 mg/day doses (see above). Using a double-blind design, half of the participants in each group will be administered amisulpride, whereas the other half will receive placebo.

c. Devices to be used

Not applicable

d. Surgical interventions

Not applicable

e. Data to be collected

Please see below for details on data collected and analyses performed.

VI. BIostatistical Analysis

a. Specific data variables being collected

Probabilistic Reward Task (PRT)

The main variable is response bias, which assesses participants' preference for the stimulus paired with more frequent reward, and will be calculated using a published formula ([name] et al 2005). To test the specificity of findings, control analyses will be run on discriminability, which provides a measure of the ability to discriminate the two stimuli. To test **Hypothesis 3a** and **3b**, *Group* (CSA/MDD, CSA/RES, MDD, controls) x *Block* (1,2,3) ANOVAs will be run for response bias and discriminability.

Implicit Learning Serial Reaction Time Task (SRTT)

SRTT data will be analyzed using established procedures (median reaction times for blocks presenting random vs. the predetermined sequence will be calculated; (Kathmann et al, 2005). If group differences emerge in procedural learning, SRTT data will be used as covariates/regressors in all analyses.

Optimism Bias Task

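### As written, Hypothesis 1c has no on-drug measurement and no Drug contrast: the Optimism Bias Task is scheduled only at the PET visit, while the single dose is given at the fMRI visit

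*Combined protocol and SAP*

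**What the plan says.** Section II, Specific Aim 1, lists two hypotheses on this task. Hypothesis 1c is that raised phasic dopamine release through amisulpride "will re-orient MDD individuals from a pessimistic outlook to an optimistic outlook as measured by the Optimism Bias Task". Hypothesis 1d is that "under placebo, MDD participants will show a pessimistic outlook as compared with healthy controls".

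Section V.a, PET Session, is the only place that assigns the task to a visit. At the Massachusetts General Hospital PET facility, before the scan, "participants will complete two tasks on cognitive functioning: the Optimism Bias Task, and the Self-Concept Attention Task".

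Dosing belongs to a different visit. Of the fMRI session, Section V.a says: "This session will take place at the McLean Hospital Imaging Center". Amisulpride or placebo is taken there one hour before scanning. The Randomization text says that the study "involves a single MRI session, and does not include a treatment component", and Section V.b that "half of the participants in each group will be administered amisulpride, whereas the other half will receive placebo".

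Section V.a leaves the order of the fMRI, PET and ERP sessions to facility availability and participants' convenience. It gives no interval between them.

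Section VI.a, Optimism Bias Task, defines an update score (second estimate minus first) and compares good-news with bad-news trials. It names neither Drug nor Group.

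**The concern.** Hypothesis 1c is a randomised, acute drug-effect hypothesis, so its outcome has to be measured while the randomised condition is in force. As scheduled, it is measured at a visit where nobody is dosed. Some participants may do the task before they have received anything. For them an amisulpride-versus-placebo split can show only chance differences. Others may do it an unstated number of days after the dose. The protocol gives the time to first peak plasma concentration (1 to 1.5 hours) but no elimination time, so carry-over to the PET visit can be neither assumed nor excluded.

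The risk is that a split of these scores by arm is reported as a test of Hypothesis 1c. A larger sample or a better model would not cure that. Choosing the contrast now is also delicate because, according to the Randomization text, "the blind was broken as of May 2016 to conduct preliminary analyses". Any contrast added later needs a date and a label.

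**Working it through.** The plan gives no figure for Hypothesis 1c, so the main check is a comparison of sections.

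**1. Where the task is.** It appears in the PET Session section. The fMRI Session text lists the serial reaction time task, the Self-Concept task, the MID and the PSST, but not this one.

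**2. Where the dose is.** It is given in the fMRI session only, once per participant. Asymptomatic participants leave three hours after dosing.

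**3. Whether the two visits coincide.** The sites differ. Section III puts pregnancy tests at sessions 1, 3 and 4, and Section IX.b calls session 3 the fMRI session, so the two visits are numbered separately. Same-day visits are not forbidden, but nothing plans them.

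**4. Whether the re-estimation could be on drug.** The task description has participants re-rate the 40 events in a second session without naming a visit. It also gives the whole task about 30 minutes, which favours one sitting.

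**5. Whether a Drug term exists.** Section VI.a has two Drug models: Group x Drug x Trial Type for PSST and MID behaviour, and Group x Condition x Hemisphere x Trial for fMRI beta weights. Neither includes this task, and Section VI never cites Hypotheses 1c or 1d.

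**6. Size for Hypothesis 1c.** Planned amisulpride recipients: 92 / 2 = 46. Number scheduled to do the task in the dosing session: 0.

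**7. Size for Hypothesis 1d.** With 23 per group and a 50:50 split, each group has 11 or 12 on placebo. Pooling CSA/MDD with MDD gives about 23 depressed participants on placebo against 11 or 12 controls.

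Power is for a two-sided two-sample t-test at alpha 0.05 (noncentral t), with df = n1 + n2 - 2 and noncentrality d x sqrt(n1 n2 / (n1 + n2)). For 23 vs 12 the multiplier is sqrt(276/35) = 2.81.

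| Comparison | Power at d = 0.50 / 0.60 / 0.70 | Detectable d, 80% power |
|---|---|---|
| Placebo arm, pooled, 23 vs 12 | 0.28 / 0.37 / 0.48 | 1.03 |
| Placebo arm, pooled, 23 vs 11 | 0.26 / 0.36 / 0.46 | 1.06 |
| No amisulpride before the task, upper limit, 46 vs 23 | 0.49 / 0.64 / 0.77 | 0.73 |

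The last row applies only if every PET visit came before the dose. If every PET visit came after it, that set shrinks to the placebo arm. The d values are assumptions: the power section has no effect size for this task, and 0.70 is its figure for MDD versus controls on the probabilistic reward task.

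**8. Sign of the score.** Let g and b be the sizes of the moves toward good and bad news. Good news lowers the estimate, so second minus first is -g; for bad news it is +b. Good minus bad of these signed scores is -g - b = -(g + b). For illustrative (g, b) of (15, 5), (10, 10) and (5, 15) it is -20 each time, whereas the asymmetry g - b is +10, 0 and -10.

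**The case against.** The strongest reply is that the PET listing is a clerical error. This is plausible. The same sentence lists the Self-Concept task, which its own section places in the fMRI session with the EEG session as fallback, so the PET task list is visibly unreconciled. A reader might infer from the schedule that no on-drug optimism data exist. The documents do not support that: they show what was planned, not what was done. The slip would explain the visit, but it would not supply the missing Drug contrast.

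A reader might also infer that Hypothesis 1d fails for the same reason, since no placebo is given at the PET visit. That goes too far. Randomisation is between subjects, so the phrase can mean the placebo arm. Those participants never receive amisulpride, and comparing MDD with controls among them is free of the drug whenever PET takes place.

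Nor can the scoring be called wrong. Section VI.a states a signed update and a comparison of good-news with bad-news trials, but not a good-minus-bad subtraction, and it also speaks of the extent of change, which could mean magnitude. A request to clarify is all that stands.

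Finally, the power figures describe Hypothesis 1d, not the defect in Hypothesis 1c, which is one of validity.

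**Conclusion.** The conflict stands on the text. If the plan is followed as written, Hypothesis 1c cannot be tested: 0 of about 46 planned amisulpride recipients do the task in the dosing session, and no model contains the contrast. This assumes that the PET listing is literal and that the two visits fall on different days. Both can be checked against visit records.

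The point should be fixed, but its reach is limited. It concerns one hypothesis under Aim 1, with a possibly clerical cause. Hypothesis 1d remains testable in the placebo arm, with low power. Those figures use the planned 23 per group; enrolment requires only at least two completed imaging sessions, so fewer may have task data. Hypotheses 1a and 1b and Aims 2 to 4 are untouched.

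**What to change.** 1. **Reconcile the sections** on Hypotheses 1c and 1d, the Self-Concept task, the PET session, the Optimism Bias Task and its analysis, using visit records. Record for each participant whether the task came before or after dosing, and by how many days.
2. **Hypothesis 1c.** For data collected at the PET visit, keep it listed and report it as not validly testable; any split by arm is exploratory. If records show the task was run after dosing at the fMRI visit, correct the PET section and state a Group x Drug x news (good, bad) model with the Drug contrast in MDD, dated and labelled as added after the blind was broken.
3. **Hypothesis 1d.** Keep MDD versus controls in the placebo arm as the main comparison, and say whether CSA/MDD is included. Add a secondary analysis of all participants with no amisulpride before the task. Report estimates with confidence intervals.
4. **Scoring.** As a clarification, score updates toward the information given: first minus second for good news, second minus first for bad news. Bias is then good minus bad.

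The cost is a dated amendment, two timing variables and one line of scoring code; no data are lost. The downside is that Hypothesis 1c gets no valid test from PET-visit data and the main Hypothesis 1d comparison is small. The secondary set gains power only to the extent that PET preceded the dose.

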
concentrations of electrolytes, BUN, SGOT, SGPT, CPK, alkaline phosphatase, total bilirubin, albumin, total protein, blood pregnancy test, TSH, eGFR, and electrocardiogram (EKG), and a urine drug test. These tests must be performed within four weeks prior to amisulpride administration.

Preliminary screening for sex, handedness, neurological disorders, exclusionary physical conditions, medication status, weight, history of childhood trauma and history of depression, and MRI and PET safety will take place at the time of the initial telephone contact or interview or via the online screening survey on RedCap (a Partners secure website). Subjects will be re-screened for MRI safety at the beginning of the fMRI session.

To avoid the confounding effects of medication, only subjects off medication will be considered. Importantly, no subject will be requested to discontinue treatment for the purpose of participating in the studies proposed here. Further, if any subject becomes emergently ill or suicidal, access to emergency clinical care will be provided according to established procedures at McLean Hospital. If at any point between signing of consent and the conclusion of the second session, a subject becomes suicidal, homicidal, manic, or psychotic, (s)he will be withdrawn from the study and appropriate care and resources will be provided. Depending on the outcome of the first session, eligible participants will be assigned to one of four groups: (1) CSA between the ages of 5-14 with current diagnosis of MDD (*CSA/MDD*), (2) CSA between the ages of 5-14 without current or past diagnosis of Axis I or II disorders (*CSA/RES*), (3) current diagnosis of MDD without a history of CSA (*MDD*), and (4) healthy controls. Each group will contain 23 subjects who complete at least two imaging sessions (n=23/group).

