The PSST task (Frank et al, 2004) will allow us to examine whether participants exhibit a bias for choosing frequently reinforced stimuli or avoiding frequently punished stimuli, and thus to assess positive and negative reinforcement learning. Of note, this task has been found to be sensitive to DA modulations, suggesting that hypodopaminergic states affect phasic DA signals required for learning from positive outcomes. Thus, MDD subjects are expected to be better at learning from punishment than reward in the PSST. The task has two phases: a learning and testing phase. In the learning phase, subjects are randomly presented with three different stimuli pairs (AB, CD, EF), and are instructed to choose one of the two stimuli by pressing a key. After the response, feedback is given to indicate whether the choice was correct or incorrect. Importantly, the feedback is probabilistic: for AB trials, a choice of stimulus A leads to positive feedback in 80% of the trials, while a choice of stimulus B leads to negative feedback in 80% of the trials. The stimulus pair CD is less reliable, with stimulus C being correct in 70% of the trials, and the stimulus pair EF is the least reliable, with stimulus E being correct in 60% of the trials. Subjects learn to choose stimuli A, C, and E more frequently than B, D, or F, during the learning phase. Of note, learning to choose A over B can be achieved either by learning that

A usually leads to positive feedback or that B usually leads to negative feedback, or both. The learning phase ends after participants reach performance criteria (65% accuracy for A, 60% for C, and 50% for E) or after 6 blocks. The performance criteria are set so that all subjects are at the same level before starting the testing phase. In the testing phase, the same three pairs as well as all novel combinations of stimuli pairs are presented, and no feedback is provided. To examine whether subjects learned more about positive or negative outcomes of their decisions, the stimuli pairs of interest are those involving an A or B stimulus paired with a novel stimulus (e.g., AC, AD, BC, BD), referred to as transfer pairs. These transfer pairs will allow us to assess whether subjects learn from prior positive feedback to choose the most reinforced stimulus (“Choose A”) or learn from prior negative feedback to avoid the most punished stimulus (“Avoid B”).

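### The drug blind is broken before data collection ends, and the stated precaution covers the testing of added participants but not the decisions to drop or replace data

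*Combined protocol and SAP*

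**What the plan says.** Section V, Randomization, describes a double-blind, between-subject comparison of one amisulpride dose with placebo, split half and half within each of the four groups. On the blind it states: "Though data collection has not yet been completed, the blind was broken as of May 2016 to conduct preliminary analyses". The next sentence gives a second date: "Accordingly, the medication blind will be broken as of November, 2016 in order to allow further analyses".

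The precaution offered is that the research assistant running participants, the study doctors and any other laboratory member "who directly interacts with participants will remain blind to drug group assignment". The plan applies this to one case, described as "if we discover during statistical analyses that a few participants yielded unusable data (e.g., due to excessive motion artifacts". Its conclusion for that case is that "we will be able to enroll and test a few final participants in a fully unbiased way".

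Other sections touch on data quality or numbers:

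- The MRI acquisition paragraph in Section V.a specifies prospective motion correction.
- Section VI.a, fMRI Analyses, lists motion correction among the pre-processing steps.
- Section IV.a sets the target: "Each group will contain 23 subjects who complete at least two imaging sessions (n=23/group".
- Section VI.d arrives at 92 subjects after allowing for 5% data loss.

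**The concern.** Blind testing of a late participant and blind selection of the analysis set are different protections, and the precaution supplies only the first. Three things remain open: who judges that a dataset is unusable, by what limit, and what then triggers a replacement. The plan places the discovery of unusable data within statistical analysis, for which it has broken the blind. Those judgements can therefore be made by people who know both arm and results.

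A drug test at the 0.05 level keeps that level only if exclusion and replacement do not depend on arm or result. Judging motion without knowing the arm is not enough: flags unrelated to outcome still raise the error rate if they are acted on only when the first result disappoints. The plan as written gives no basis for telling which course was followed.

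The tests at stake are the amisulpride v placebo comparisons, mainly the MID task in fMRI and the PSST and MID behaviour. The group-only PET and ERP comparisons do not depend on the drug blind.

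**Working it through.** **Is there a rule elsewhere?** Each place that might supply one was checked.

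- Section V.a, MRI acquisition: motion is corrected prospectively; no limit for exclusion.
- Section VI.a, fMRI Analyses: motion is corrected in pre-processing; no limit for exclusion.
- Section IV.a, enrolment target: counts completion of at least two imaging sessions, which does not define usable data.
- Section IV.a, skin biopsy: has a substitution rule, but only for prioritising cell conversion.
- Section VI.d: allows 5% loss but does not say what loss leads to replacement.
- Section V, Randomization: names who stays blind. Analysts and usability raters are not among them.

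**Inputs.** The plan gives no error rate for this procedure, so its nominal 0.05 (Section VI.d) is the reference. Each group of 23 splits as 23 / 2 = 11.5, taken as 12 v 11. Section VI.d names CSA/MDD on drug v placebo as a sample-size contrast. The plan gives no flag rate; 5% and 10% are assumed. The first equals the planned data loss: 0.05 x 92 = 4.6 datasets overall, or 0.05 x 23 = 1.15 per group. The second gives 0.10 x 92 = 9.2.

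**Model.** Outcomes are normal with no drug effect, and the test is a pooled two-sided t-test at 0.05. Each dataset is flagged independently of its outcome, and replacements are drawn in the same arm. There were 400,000 runs per cell, with a Monte Carlo standard error of about 0.04 points. The t-test is a stand-in for the planned Group x Drug x Trial ANOVAs.

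Under a result-dependent rule,

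error = P(first p < 0.05) + P(first p >= 0.05 and second p < 0.05).

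The first term is 5%; the second is the excess.

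| Rule, 12 v 11 | 5% flagged | 10% flagged |
|---|---|---|
| All flagged replaced, whatever the result | 4.96% | 4.99% |
| All flagged excluded, not replaced, whatever the result | 4.97% | 4.98% |
| Flagged replaced only if first p >= 0.05 | 6.14% | 6.89% |
| Flagged excluded, not replaced, only if first p >= 0.05 | 5.85% | 6.44% |
| Selective, hypothesised direction | 5.69% | 6.37% |
| Selective, observed direction | 6.37% | 7.64% |

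In the selective rows, after a non-significant first look, at most one dataset per arm is replaced: the worst flagged one on the unfavourable side of its arm mean.

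The first two rows reproduce the nominal 5%. The smallest excess is 5.69 - 5.00 = 0.69 points and the largest is 7.64 - 5.00 = 2.64 points. A repeat with a different random seed agreed to within 0.1 point.

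The effect is not confined to small subgroups. With the groups pooled, 46 v 46, replacement only after a non-significant look gives about 6.3-7.1%.

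**The case against.** The strongest reply is that the plan's stated trigger is unusable data, not a disappointing result, and under that trigger the simulation gives 5.0%. Every figure above 5% rests on a rule the plan does not contain. Motion, the only example given, can be judged without knowing the arm. This stands as a limit on the size of the problem. It does not remove it, because the plan neither states that replacement is independent of results nor puts the judgement in blind hands.

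A reader might infer more than the text supports:

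- *That bias occurred.* Nothing in the documents shows a selective exclusion or replacement.
- *That replacements are decided during unblinded analysis.* The plan says only that unusable data may be discovered then, and that enrolment can follow. Who decides, and when, is left open.
- *That enrolment may be extended until a result is significant.* The plan ties added participants to unusable data and proposes no extension.
- *That error rates could reach 8.5-15.0%.* That range arises at 11 v 12 only if the one to three least favourable amisulpride values are deliberately replaced after a non-significant look. Nothing in the documents suggests this.

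The plan also describes a proof-of-mechanism study without a treatment component. That limits the consequences, but the plan itself calls the design double-blind and offers the precaution to protect scientific integrity. Multiplicity across regions and tasks, and the handling of PSST participants who miss the learning criterion, are separate matters and are not counted here.

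**Conclusion.** The concern holds as a gap in procedure, and the text should be changed. The precaution supports the statement that added participants are tested blind. It does not support the wider statement of full unbiasedness for the amisulpride v placebo tests, because decisions on exclusion and replacement are left without a limit, a blind rater or a trigger.

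The size is conditional. There is no excess if flags are always acted on. The excess is about 0.7-2.6 percentage points per test at 12 v 11 if they are acted on only after a non-significant look. This assumes flag rates of 5-10%, flags unrelated to outcome, and a two-arm t-test in place of the planned ANOVAs. No sample size or power figure changes.

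**What to change.** (a) Before further unblinded analysis, have staff who have not seen results by arm set numeric motion and artefact limits for fMRI and data-quality limits for the behavioural drug outcomes. Have existing staff without access to allocation or results apply them to every dataset, including those already analysed, and lock the list. The plan does not identify such raters, so they must be designated. Replace according to the locked list and a pre-stated loss threshold, regardless of any result, with allocation concealed from those who enrol and test.

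(b) Report exclusions by arm with reasons and disclose the preliminary unblinded analyses. Give the drug analyses with and without participants enrolled after the first unblinding and, where analysable, with and without the excluded data.

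(c) Narrow the unbiasedness claim to say that testing of added participants is blind, and clarify whether May and November 2016 are separate unblindings.

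The cost is one blinded quality-control pass, one sensitivity table and a few sentences. The downside is that some datasets already analysed may be excluded, and replacement may be required even where results already look favourable.
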